6.1 Timing of Analyses

An interim analysis is planned to be performed in June 2021.

The final analysis will be performed in July-September 2021.

6.2 Analysis Populations

All enrolled participants who met the eligibility criteria and with data available at baseline will be included in the Full Analysis Population. The primary endpoint and all secondary endpoints will be analysed on this Full Analysis population.

7. Summary of Study Data

All continuous variables will be summarized using the following descriptive statistics: n (non-missing sample size), mean, standard deviation, 1st quartile, median, 3rd quartile, maximum and minimum. The frequency and percentages (based on the non-missing sample size) of observed levels will be reported for all categorical variables.

7.1 Subject Disposition

The number of patients and the flowchart of the study will be presented. The period of enrolment will be given. The number of patients excluded, and the total number of analysed patients will be presented. The number of patients who never take the study treatment will also be given. The number of patients who did not receive the full dose of Remdesivir will also be presented. The number of participants who discharge or die before day 28 will be presented.

7.2 Demographic and baseline variables

The baseline patients' characteristics of the full analysis population will be described globally and according to the Ordinal Scale (ORDSC) clinical status at baseline (score 2 vs 3-4 vs 5)

and will be presented in a summary table. The summary statistics will be produced in accordance with section 7. Non-parametric Kruskal-Wallis test will be used to compare continuous variable between the 3 groups and Chi-square test for categorical variables. P-values will be two-tailed with a significant level at 5%.

This table will be structured as follows:

8. Efficacy Analyses

8.1 Primary Efficacy Analysis

Primary endpoint	
 Occurrence of death within 28 days
Analysis population	
 Full population analysis
Descriptive statistics and graphical representation	
 Data will be summarized with proportion and 95% confidence interval globally and according to disease severity at baseline (ORDSC score 2 vs 3-4 vs 5) LogRank test will be used to compared the 3 groups P-values will be two-tailed with a significant level at 5%. Kaplan-Meier curves will be plotted
Statistical analysis	
Kaplan-Meier estimates will be used to calculate the proportions and the 95% confidence intervals
 
Time to death will be defined as the time between the date of hospitalization and the date of death or discharge from hospital or last observation
 
Participant with missing clinical status or alive at day 28 will be censored at the date of last observation

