	
 7.1. Frequency of mechanical ventilation/ECMO 7.2. Time (days) on mechanical ventilation/ECMO 8. Duration (days) of hospitalisation 9. Timing of use of Remdesivir 
 9.1. Time (days) from first symptoms to use of Remdesivir 9.2. Time (days) from hospitalisation to use of Remdesivir 9.3. Duration (days) of use of Remdesivir 10. Re-admission within the 28 days following discharge 
 10.1. Frequency of re-admission with COVID-19 within 28 days of discharge 10.2. Frequency of discharge after re-admission 10.3. Frequency of death after re-admission
--	---------------------------------------------------------------------------------------------------------------------------------------------------------------------------------------------------------------------------------------------------------------------------------------------------------------------------------------------------------------------------------------------------------------------------------------------------------------------------------------------------------------------------------------------------------------------------------------------------------------------------------------------------------------------------------------------------------------------------------------------------------------------------------------------------------------------

4. Study Methods

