4.2 Study Variables

All the study variables are summarized in the following table.

	Day1 (Hospital Admission) baseline	Day 7 (+/- 1 day) and Day14 (+/- 2 days) / last observation if discharged or died prior to these time points.	Day 28 or last observation after Day 14 if discharged or died prior to this time point.
Medical History ^a	x		
Pregnancy test	x		
HIV test	x		
Vital Signs ^b	x	x	x
Laboratory Testing ^c	x	x	x
Oxygenation ^d	x	x	x
Clinical Status ^e	x	x	x
Other Treatments for COVID-19 ^f	x	x	x
NEWS SCORE ^g	x	x	x

a. Focused medical history and also the following information (e.g. demographics including ethnicity, baseline characteristics including DM, CV disease and COPD)

b. SpO2, body temperature, body weight and height on admission

c. Includes white blood cell count, creatinine, total bilirubin, ALT, AST at admission Day 7 and day 14 or at discharge if before day 14, radiographic findings at baseline and as available and SARS-CoV-2 PCR, antigen and/or antibody testing.

d. Includes oxygen supplementation: room air, low flow O2 (L/min and %), high flow O2 (L/min and %), non-invasive positive pressure ventilation (FiO2 or %), mechanical ventilation (FiO2 or %), ECMO (extracorporeal membrane oxygenation)

e. The ordinal scale is as: 1. Death, 2. Hospitalised, on invasive mechanical ventilation or ECMO, 3. Hospitalised, on non-invasive ventilation or high flow oxygen devices, 4. Hospitalised, requiring low flow supplemental oxygen, 5. Hospitalised, not requiring supplemental oxygen - requiring ongoing medical care (COVID-19 related or otherwise), 6. Hospitalised, not requiring supplemental oxygen - no longer requires ongoing medical care, 7. Not hospitalised

f. These include corticosteroids, anticoagulants, azithromycin/other antibiotics, anti-inflammatory agents (e.g. Tocilizumab), investigational agents (eg hydroxychloroquine) and immunotherapies such as convalescent plasma and monoclonal antibodies.

g. NEWS 2 score is based on Respiration rate (per minute), SpO2 (%) Air or oxygen. Systolic blood pressure (mmHg), Pulse (per minute) Consciousness, Temperature (°C)

For the purpose of the analyses, partial dates will be extrapolated. For example, all dates saved as NK/FEB/2020 will be recoded as 15/FEB/2020 and those saved NK/NK/2020 will be recoded as 15/JUNE/2020. NK means not known.

5. Sample Size calculation

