8.2 Secondary Efficacy Analyses

Endpoint	
 Disease state on a 7-point scale at Day 7, 14 and 28 (or last observation if discharged or died prior to this time point) defined as: 
 death, hospitalized, on invasive mechanical ventilation or ECMO, hospitalized, on non-invasive ventilation or high flow oxygen devices, Hospitalized, requiring low flow supplemental oxygen, hospitalized, not requiring supplemental oxygen - requiring ongoing medical care (COVID-19 related or otherwise), hospitalized, not requiring supplemental oxygen - no longer requires ongoing medical care, not hospitalized
----------	-------------------------------------------------------------------------------------------------------------------------------------------------------------------------------------------------------------------------------------------------------------------------------------------------------------------------------------------------------------------------------------------------------------------------------------------------------------------------------------------------------------------------------------------------------------------------------------------------------------------------------------------------------------------------------------------------------------------------------------

Analysis population	
 Full population analysis
Descriptive statistics and graphical representation	
 Data will be summarized with proportion and 95% confidence interval globally and according to disease severity at baseline (ORDSC score 2 vs 3-4 vs 5) Proportional odds models will be used to compared the 3 groups P-values will be two-tailed with a significant level at 5%.
Statistical analysis	
The proportions will be calculated by the number of subjects in each category divided by the total number of subjects in the full analysis population.
 
Subjects with missing clinical status will be considered deceased
 
The associated two-sided 95% exact confidence intervals will be calculated using Clopper–Pearson method

Endpoint	2. Disease severity at day 7, 14, and 28 as assessed by NEWS 2 score
Analysis population	
 Full population analysis

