Descriptive statistics and graphical representation	
 • Data will be summarized with proportion or median and 95% confidence interval according to the endpoint • Data will be summarized globally and according to disease severity at baseline (ORDSC score 2 vs 3-4 vs 5) • LogRank test will be used to compared the 3 groups • P-values will be two-tailed with a significant level at 5% • Kaplan-Meier curves will be plotted
Statistical analysis	
Kaplan-Meier estimate will be used to estimate the proportion of subject with oxygen therapy and by type (low versus high flow oxygen), the proportion of subjects admitted in ICU and the proportion of those having received mechanical ventilation or ECMO. Time to event will be defined as the time between the date of first symptom and the date of event of interest. Participants not experienced the event of interest will be censored at last observation date. Participants who deceased before will be considered as having the event.
 
The duration (days) of oxygen therapy, the number of days spent in ICU/ITU and the time (days) on mechanical ventilation/ECMO will be estimated using Kaplan-Meier estimates as well as the associated 95% confidence intervals. The time will be defined as the time between the start date of event and the end date of the event of interest or hospital discharge. Subjects who died will be censored at day 28.

Endpoint	8. Duration (days) of hospitalization
----------	----------------------------------------------

Analysis population	
 Full population analysis
Descriptive statistics and graphical representation	
 Data will be summarized with median and 95% confidence interval globally and according to disease severity at baseline (ORDSC score 2 vs 3-4 vs 5) LogRank test will be used to compared the 3 groups P-values will be two-tailed with a significant level at 5% Kaplan-Meier curves will be plotted
Statistical analysis	
Kaplan-Meier method will be used to calculate the medians and the 95% confidence intervals. Time (days) from hospitalization to hospital discharge will be defined as the time between the date of hospitalization for COVID-19 and the date of hospital discharge. The event will be hospital discharge. Subjects who died will be censored at day 28.

9. Other Analyses

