Endpoints	9.1. Time (days) from first symptom to use of Remdesivir 9.2. Time (days) from hospitalization to use of Remdesivir 9.3. Duration (days) of use of Remdesivir
Analysis population	
 Full population analysis
Descriptive statistics and graphical representation	
 Data will be summarized with median and 95% confidence interval globally and according to disease severity at baseline (ORDSC score 2 vs 3-4 vs 5) LogRank test will be used to compared the 3 groups P-values will be two-tailed with a significant level at 5% Kaplan-Meier curves will be plotted.
Statistical analysis	
Kaplan-Meier method will be used to calculate the medians and the 95% confidence intervals of the time to use of Remdesivir. Time (days) from first symptom to use of Remdesivir will be defined by the time between the date of first symptom and the start date of Remdesivir. The event will be the exposure to Remdesivir therapy at least one time during the hospitalization period
 
The time (days) from hospitalization to the use of Remdesivir will be estimate using the Kaplan-Meier method as well as the 95% confidence interval. The event will be the first use of Remdesivir.
 
Duration (days) of use of Remdesivir will be estimated using the Kaplan-Meier method. The time is defined as the time between the start date of Remdesivir and the end date of Remdesivir. The event will be the discontinuation of the use of Remdesivir.

Endpoints	10.1. Frequency of re-admission with COVID within 28 days of discharge 10.2. Frequency of discharge after re-admission 10.3. Frequency of death after re-admission
Analysis population	
 For 10.1, the analysis population will be all subjects who discharge from hospital within the first 28 days For 10.2 and 10.3, the analysis population will be all re-admitted subjects
Descriptive statistics and graphical representation	Data will be summarized with number of subjects with an event out of the total number of analyzed population Data will be summarized globally and according to disease severity at baseline (ORDSC score 2 vs 3-4 vs 5) Chi square test will be used to compared the 3 groups P-values will be two-tailed with a significant level at 5%

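### The primary Day-28 mortality estimate censors patients discharged alive at discharge, which pushes the Kaplan-Meier percentage upward if risk falls after discharge

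*SAP*

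**What the plan says.** SAP 3 sets one primary endpoint, death from any cause within 28 days, and does not limit it to deaths in hospital. SAP 8.1 and Protocol 6.3 both estimate it by Kaplan-Meier. The protocol gives no censoring rule. SAP 8.1 gives two sentences:

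- On the time scale: "Time to death will be defined as the time between the date of hospitalization and the date of death or discharge from hospital". The sentence then adds last observation as a third end point.
- On censoring: "Participant with missing clinical status or alive at day 28 will be censored at the date of last observation".

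Several other places bear on this:

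- The last column of the schedule in SAP 4.2 is "Day 28 or last observation after Day 14 if discharged or died prior to this time point". A patient discharged early therefore need not have a Day-28 record.
- Some information after discharge is planned. SAP 3 endpoint 10.3 is "Frequency of death after re-admission", and in SAP 9 "For 10.1, the analysis population will be all subjects who discharge from hospital within the first 28 days".
- For duration of hospitalisation (SAP 8.2, endpoint 8), where death is the competing event, the rule is explicit: "The event will be hospital discharge. Subjects who died will be censored at day 28". SAP 8.1 has no rule of this kind for live discharge.

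**The concern.** Kaplan-Meier is valid when censored patients have the same later risk as those who remain under observation. Discharge usually selects patients who are recovering, so censoring there is likely to be informative. The estimate then answers what mortality would be if every discharged patient kept the inpatient death risk up to Day 28. That is not all-cause Day-28 mortality, and the confidence interval is centred on the wrong quantity.

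The SAP tests no formal hypothesis, so this percentage is the study's main result. It goes into Table 2 overall and for each baseline severity group. Because the bias depends on how fast patients leave hospital, groups with equal mortality but different stays would show different percentages.

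A second gap follows. The rule does not say how to count a death on or before Day 28 that is recorded after a first discharge, for example after re-admission. A clock that stops at first discharge leaves it out.

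**Working it through.** The plan states no expected mortality, discharge rate or length of stay, so there is no figure to reproduce. The only input from the documents is n = 450. Everything else is an assumption.

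**Model.** Constant hazards over 28 days:

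- Total exit hazard H = ln 2 / median stay, where stay is time to death or discharge.
- Share who have left by Day 28: F = 1 − exp(−28H).
- With no deaths after discharge and true mortality m, the inpatient death hazard is hd = H·m/F and the discharge hazard is H − hd.
- Kaplan-Meier with censoring at discharge converges to 1 − exp(−28·hd).

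**Worked case: m = 10%, median stay 10 days.** H = 0.6931/10 = 0.0693. F = 1 − exp(−1.941) = 0.856. hd = 0.0693 × 0.10/0.856 = 0.00809. Discharge hazard = 0.0612. SAP estimate = 1 − exp(−28 × 0.00809) = 20.3%. By Day 28, 10.0% have died, 75.6% have been discharged and 14.4% are still in hospital.

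**Deaths after discharge.** Let k be the post-discharge death hazard divided by the inpatient hazard. Then hd is solved so that hd·F/H plus the integral from 0 to 28 of (H − hd)·exp(−H·u)·[1 − exp(−k·hd·(28 − u))] du equals 10%. Median stay is again 10 days:

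| k | In-hospital deaths | SAP estimate | Ratio to true 10% |
|---|---|---|---|
| 0 | 10.0% | 20.3% | 2.03 |
| 0.1 | 9.0% | 18.4% | 1.84 |
| 0.25 | 7.8% | 16.2% | 1.62 |
| 0.5 | 6.4% | 13.4% | 1.34 |
| 1.0 | 4.7% | 10.0% | 1.00 |
| 1.5 | 3.7% | 8.0% | 0.80 |

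**Length of stay (k = 0, true 10%).** Median stays of 5, 10 and 20 days give 32.7%, 20.3% and 14.5%.

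**Corners of the grid (k = 0, true 5 to 30%, stay 5 to 20 days).** The lowest ratio is 1.25 (true 30%, 20 days: 37.4%). The highest is 3.60 (true 5%, 5 days: 18.0%).

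**Second parameterisation.** Here the in-hospital death and live-discharge proportions by Day 28 are fixed instead. With 10% and 80%, the SAP estimate is 22.6%, against a truth of 10.0% at k = 0, 11.4% at k = 0.1 and 16.6% at k = 0.5. Over six such pairs, from 5%/85% to 30%/40%, the bias at k = 0.5 is 3.4 to 6.3 points.

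**Sampling behaviour.** Simulated cohorts of 450 (true 10%, 10-day stay, k = 0) gave a mean SAP estimate of 20.3% with a standard error of about 3.1 points. Keeping discharged patients at risk to Day 28 gave 10.0% and 1.4 points. The log-log 95% interval under the SAP rule contained the true 10% in about 2 to 3% of cohorts.

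**The case against.** **The text does not say outright that live discharges are censored at discharge.** The one explicit censoring sentence could be read as letting a patient known to be alive on Day 28 be censored then. But it censors at last observation, the schedule lets that precede Day 28 for discharged patients, and the time definition stops at discharge. At best the two sentences conflict, and a primary analysis should not depend on which one the programmer follows.

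**The contrast with duration of hospitalisation is imperfect.** This is correct. Death rules out later discharge, so holding deaths to Day 28 there needs no unseen data. Discharge does not rule out later death. The contrast shows only that the SAP treats the competing event elsewhere; the concern does not depend on it.

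**The size is assumed, and the hazards need not be constant.** This stands. With deaths concentrated early, the ratio at 10% in-hospital death and a 10-day median time to discharge falls to about 1.6, and later deaths raise it. The 3.60 figure is a corner case.

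**Holding discharged patients to Day 28 can be just as wrong if their deaths are not recorded.** This is the most important objection. At k = 0.5 with no post-discharge death captured, that rule gives 6.4% against a true 10%, an error of −3.6 points; the SAP rule gives 13.4%, an error of +3.4. The remedy therefore depends on whether vital status is known.

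**Other outputs would show the gap.** Table 2 also gives the count of deaths by Day 28, and SAP 7.1 says "The number of participants who discharge or die before day 28 will be presented". The Day-28 ordinal proportions give another view, although there "Subjects with missing clinical status will be considered deceased". These reveal a discrepancy but do not correct the labelled primary estimate.

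**Conclusion.** The concern holds. As written, SAP 8.1 ends follow-up at live discharge, and the resulting Kaplan-Meier percentage does not estimate all-cause Day-28 mortality unless death risk is the same after discharge as before. The direction is upward whenever post-discharge risk is lower, which is the expected situation but cannot be shown from the documents.

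The size cannot be fixed either. For true mortality of 10% and a 10-day median stay under constant hazards, the estimate is between 13.4% and 20.3% for a post-discharge hazard from half the inpatient level down to zero.

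The log-rank comparison of severity groups is not invalidated. It compares in-hospital death hazards, which is a different question from Day-28 mortality. Because this is the SAP's only primary endpoint, the rule must be corrected before the result is reported.

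**What to change.** First check whether the eCRF holds vital status and date of death after discharge, including deaths after re-admission.

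**If it does,** put this rule in SAP 8.1: subjects discharged alive are censored at day 28 unless a death on or before day 28 is recorded, including after re-admission, in which case that death is the event at its date. Reword the existing censoring sentence to agree. Add a sensitivity analysis for patients whose status after discharge is unknown, for example assuming that 1%, 2% or 5% of them died by Day 28.

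**If it does not,** either collect that field or report the Aalen-Johansen cumulative incidence of in-hospital death, with live discharge as a competing event, and rename the endpoint in-hospital mortality. This is a different estimand: 6.4% in the k = 0.5 case above.

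The log-rank test, and the Cox model in Protocol 6.3 if it uses the same time scale, may stay if labelled as comparisons of in-hospital death hazards.

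**Cost.** A wording change and an eCRF check, plus data collection or relabelling if the field is missing. The day-28 rule assumes no unrecorded deaths between discharge and Day 28. With 75.6% discharged, unrecorded deaths in 1%, 2% or 5% of them would add 0.756 × 1, 2 or 5 = 0.8, 1.5 or 3.8 points to the true figure.

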4 ELIGIBILITY CRITERIA

4.1 Inclusion criteria

Diagnosis and Main Eligibility Criteria - Cases(Part 1)

All Adult participants with COVID-19 confirmed by PCR who meet the following criteria:

1. Hospitalised after August 31st, 2020
2. Received at least one dose of Remdesivir (RDV) at any time during hospitalisation

Diagnosis and Main Eligibility Criteria –Controls (Part 2)

Adult participants with COVID-19 confirmed by PCR who meet the following criteria:

1. Hospitalised after August 31st 2020

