6 STATISTICS AND DATA ANALYSIS

6.1 Subject population

Target Population

Adults with COVID-19 diagnosed and treated with Remdesivir after Aug 31st 2020.

Comparator group

Part 2, which is collecting data on controls, will only be initiated, if required, and once data from Part 1, the cases, is collected and analysed.

The matching criteria for controls, who were given standard of care but not Remdesivir, and who were admitted in a 2 week time window of the cases will be determined once the target population of Part 1, the cases, data has been collected and analysed.

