6.3 Statistical analysis

Summary statistics will be generated for the cohort overall and by disease severity at baseline (2 vs 3/4 vs 5). For categorical variables, numbers and percentages of participants will be reported including the 95% confidence intervals. For continuous variables, mean, standard deviation (SD), minimum, first and third quartile (Q1, Q3), median, maximum and 95% confidence intervals will be calculated, together with the total number of observations and the number of missing values. Descriptive statistics will summarize demographics and baseline characteristics. Mortality rate (all causes) at day 28 and its associated 95% confidence interval will be calculated using Kaplan-Meier estimates.

The analysis population will be consisted of all enrolled participants with data available at baseline.

We will assess factors associated with clinical status at day 14 using proportional odds models and factors associated with survival at day 28 using Cox proportional hazards models. For continuous variables, the decision to treat the variable as a continuous or categorical variable (as tertile) will be based on the lowest Akaike information criterion value for the corresponding univariable analysis. Variables achieving $P < 0.10$ in univariable analysis will be retained for the multivariable analysis.

The following variable will be assessed:

- Participating country
- Age group: < 65 vs ≥ 65 years
- Sex at birth: female vs male
- Geographic origin: European vs Sub-Saharan Africa vs. other
- Baseline clinical status (2 vs 3/4 vs 5)
- Body mass index at baseline (<18.5 vs 18.5-25; 25.01-30 vs >30 kg/m²)
- Diabetes at baseline (yes vs no)
- High blood pressure at baseline (yes vs no)
- Time from symptoms onset and date of treatment start (<7 days vs ≥ 7 days)

Secondary endpoints as well as the effect of remdesivir relative to the control group (if Part 2 is performed) will be assessed using appropriate statistical methods for non-randomized cohorts. All details of the analyses will be included in the Statistical Analysis Plan (SAP).

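### In-hospital time before the first remdesivir dose is immortal, so a Cox model timed from admission would make late treatment look protective

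*SAP*

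**What the plan says.** **Who enters.** Protocol 4.1 admits a case who "Received at least one dose of Remdesivir (RDV) at any time during hospitalisation". There is no limit on the delay.

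**When the clock starts.** The schedule in SAP 4.2 heads its first column "Day1 (Hospital Admission) baseline". SAP 8.1 states: "Time to death will be defined as the time between the date of hospitalization and the date of death". Follow-up can also end when the patient leaves hospital or was last seen. The endpoint is "Occurrence of death within 28 days", and "Kaplan-Meier estimates will be used to calculate the proportions and the 95% confidence intervals".

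**Where treatment timing is used.** Protocol 6.3 plans Cox models for factors associated with day-28 survival. One candidate factor is "Time from symptoms onset and date of treatment start", split at 7 days. The protocol gives no time origin for these models, and the SAP contains no Cox model. The SAP describes the intervals from symptoms and from admission to first dose, and the duration of use, as endpoints 9.1 to 9.3 in section 9, overall and by baseline severity.

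**Part 2.** Controls must not have received remdesivir during their stay (Protocol 4.2) and are to be "admitted in a 2 week time window of the cases" (Protocol 6.1). Part 2 is conditional. Its other matching criteria and its method of analysis are left open, and the SAP does not cover it.

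Neither document mentions delayed entry, a landmark, a clock from first dose, or time-varying exposure.

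**The concern.** Entry to the cohort depends on an event, the first dose, that can happen after time zero. Everyone in the analysis has survived the wait for that dose by construction, so the wait adds person-time but cannot contain a death.

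For the timing covariate the effect has a direction. A patient admitted on symptom day 5 is classed as early if dosed at once and as late if dosed two days later, and in the second case must have lived those two days to be counted. The late group therefore carries more death-free waiting time. Its hazard looks lower even if timing has no effect.

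The timing of remdesivir is one of the study's own secondary questions. A spurious finding that starting at day 7 or later is no worse, or is better, could be read as clinically meaningful. The same mechanism would affect a Part 2 comparison that counts treated patients from admission against patients who were never treated.

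**Working it through.** The plan has no figure to reproduce: 450 is an anticipated recruitment number with no event rate or lag behind it. All rates, lags and lengths of stay below are assumptions. The 28-day horizon, the 7-day cut and n = 450 come from the documents.

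**1. Mechanism.** Let h be a constant death hazard, W the waiting days before first dose and P the days at risk after it. Deaths can occur only in P, so the rate counted from admission is h × P/(W + P). The late/early ratio under no effect is

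[P_L/(W_L + P_L)] ÷ [P_E/(W_E + P_E)].

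Example with 28 days of follow-up, no discharge, and follow-up lost to death ignored: if late patients wait 4 days and early patients 1 day, the ratio is (24/28) ÷ (27/28) = 24/27 = 0.89. With delayed entry the rate is h × P/P = h in both groups, and the ratio is 1.

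**2. Simulation of the timing covariate, no true effect.** Constant hazard, 28-day mortality 12-18%, exponential lag from admission to dose, symptom-to-admission time averaging about 6 days. The group is symptom-to-dose ≥7 vs <7 days.

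| Mean lag | Admission clock, followed to day 28 | Admission clock, censored at discharge (mean 12 days) | Delayed entry at first dose |
|---|---|---|---|
| 1 day | 0.98 | 0.95-0.96 | 0.99-1.01 |
| 2 days | 0.94 | 0.89-0.90 | 0.99-1.01 |
| 4 days | 0.85-0.86 | 0.80-0.82 | 0.99-1.01 |

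The discharge column is included because SAP 8.1 can be read as ending follow-up at discharge. A wider run (mortality 8%, 15% or 25%; symptom-to-admission mean 5 or 7 days, SD 3; discharge mean 12 days) gave 0.95-0.96, 0.88-0.92 and 0.78-0.83 for the same lags, and 0.99-1.02 with delayed entry. With zero lag the admission clock also gave about 1 (1.00-1.02). Cox fits at 15% mortality and a symptom-to-admission mean of 7 days gave 0.945, 0.912 and 0.797 from admission, against 0.988, 1.021 and 0.998 with delayed entry (SE of the log hazard ratio about 0.05).

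**3. Size against the study's precision.** At an assumed 15% mortality, 450 × 0.15 ≈ 68 deaths. With an even split the SE of the log hazard ratio is at least √(4/68) = 0.24. A ratio of 0.89 is ln 0.89 = -0.12, or 0.5 SE. A ratio of 0.80 is -0.22, or 0.9 SE.

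**4. Primary mortality.** If 28-day mortality from first dose is m and the lag is a fixed D days, the admission clock gives 1 - (1 - m)^((28 - D)/28). For m = 15%:

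- D = 1: 14.5%
- D = 2: 14.0%
- D = 4: 13.0%
- D = 5: 12.5%

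The 95% CI half-width at n = 450 is 1.96 × √(0.15 × 0.85/450) = 3.3 points. These are two different quantities, so the gap is not in itself an error. It does mean that severity groups with the same hazard but lags of 1 and 4 days would show 14.5% and 13.0% in the planned log-rank comparison.

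**5. Part 2, if analysed from admission.** Assumptions: no treatment effect, half of patients never offered treatment, exponential discharge with mean 12 days, mortality 8-25%. Treated vs never-treated rate ratios were 0.84-0.85, 0.75 and 0.64 for mean lags of 1, 2 and 4 days. Time-varying exposure gave 0.99-1.01.

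**The case against.** Four points can fairly be made against this.

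**The primary result is descriptive.** A reader might infer that the 28-day mortality estimate itself is biased. The documents do not support that. SAP section 2 declares no hypothesis, and SAP 8.1 estimates death by day 28 of admission in patients who were eventually treated. Kaplan-Meier describes that quantity properly. It is too low only if read as mortality after starting remdesivir, or as mortality of all patients intended for it. At 15% mortality, a lag of 1 or 2 days moves it by 0.5 to 1.0 point, well inside the interval. This objection stands.

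**The Cox origin is inferred.** The admission clock in SAP 8.1 governs the Kaplan-Meier curves and the log-rank test by severity. The Cox model appears only in the protocol, without an origin. This stands too, so the bias is conditional on the analyst using the one origin that is written down. The silence is itself a gap to close.

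**Not every late patient carries immortal time.** The covariate runs from symptoms. A patient admitted on symptom day 9 and dosed at once is late but adds none. Correct: only in-hospital waiting contributes, and the documents do not say how long it is.

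**Part 2 is unfinished.** A reader might infer that any Part 2 comparison would be biased. It would not: Part 2 may never run, matching is undecided, and time-varying exposure or matching on time already in hospital would avoid the problem. Crude in-hospital deaths may also differ little (5.9% vs 6.1% at 15% mortality and a 2-day mean lag), because patients discharged before a dose also become controls. What remains is that the two features already fixed, never-treated controls and a 2-week admission window, do not remove immortal time from a hazard comparison that starts at admission.

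**Conclusion.** The point holds for the treatment-timing analysis. If the Cox model is run from admission with symptom-to-treatment time as a fixed covariate, the hazard ratio is pulled towards late treatment whenever some first doses follow admission. Under no true effect and a constant hazard, the late/early ratio is about 0.95-0.98, 0.89-0.94 and 0.80-0.86 for mean lags of 1, 2 and 4 days; the wider run extends the last to 0.78. The direction follows from the design. The size depends on a lag distribution that the documents do not give, and it is negligible if most patients are dosed on the day of admission. At 450 cases the shift is below one standard error in the 0.80-0.98 range, but it is systematic and more patients would not remove it.

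For primary mortality the point is one of labelling. For Part 2 it is a warning about a design still to be settled.

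**What to change.** **Timing and survival-factor models.** In the SAP, add the Cox model from Protocol 6.3 and state its time origin. Keep the admission clock and enter each patient at the date of first remdesivir dose (left truncation). The start date is already needed for endpoints 9.1 to 9.3, so this takes one entry variable and a sentence. State a convention for deaths on the day of first dose, so that equal entry and exit dates are not dropped by the software.

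The cost is fewer early person-days at risk and slightly wider intervals. Delayed entry also assumes that dosing delay is unrelated to death risk given the covariates. If deterioration prompts dosing, that fails, and the report should say so.

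Restarting a 28-day clock at first dose is not a clean alternative. Collection ends at Day 28 of admission, so follow-up would be cut to 28 days minus the lag.

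**Primary mortality.** Keep the Kaplan-Meier analysis. Label the result as death by day 28 of admission among patients who were eventually treated, not as mortality after starting remdesivir. Report the distribution of the admission-to-dose lag beside it, overall and by baseline severity. This costs nothing.

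**Part 2, if it runs.** Define time zero before selecting controls. Either require each control to be alive and in hospital at the matched case's first-dose time since admission and start both clocks there, or use time-varying exposure. The exclusion of anyone treated later in the stay (Protocol 4.2) still conditions on the future under the matched option and should be addressed in the same text.
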